## Protocol

### 1. Project Title:

An open label trial of sequential bifrontal low frequency repetitive transcranial magnetic stimulation (r-TMS) in the treatment of primary insomnia.

### 3. Abstract:

Transcranial magnetic stimulation (TMS) is a non-invasive brain stimulation technique that has been approved as a treatment of depression in patients that have not responded to a trial of one antidepressant medication. We hypothesize that low frequency TMS exerts inhibitory effect on hyper excitable cortical state in patients with chronic insomnia and therefore is therapeutic. Therefore, we aim to undertake this exploratory study to test this hypothesis.

**Aim:** Compare the change in insomnia scores between baseline and end of treatment in an open label trial with bifrontal low frequency TMS stimulation in 20 patients with primary insomnia using daily stimulation of 3 weeks (15 week days). **Methodology:** We aim to study 25 patients with primary insomnia to get 20 patients who complete this open label pilot study. Patients between the ages of 21-65 years who meet DSM-IV criteria for Primary Insomnia will be studied. **Results and Conclusions:** Results will be analyzed and compared between the two groups. We will also analyze the predictive value of insomnia symptoms and severity in predicting treatment efficacy of TMS. This study is innovative and first of its kind in exploring the role of TMS in chronic insomnia.

## Research Plan

### Specific Aims:

Insomnia is a common clinical problem that affects about 25 million people in the US. Insomnia exacts health and economic consequences well beyond inadequate and non-restorative sleep. It increases healthcare costs, causes or adds to medical and psychiatric comorbidities, cognitive impairments, accidents, absenteeism and reduced quality of life. Treatment of insomnia is difficult and usually needs a multimodal approach incorporating various cognitive and behavioral approaches in addition to medication treatment. TMS and other neurophysiological studies have shown presence of a diffuse cortical hyper-arousal in patients with chronic insomnia. High frequency TMS (>1 Hz) has been shown to be activating whereas low frequency TMS (<1Hz) has been shown to be inhibitory in clinical and neurophysiological studies. TMS has been approved as a treatment of depression in patients who have not responded to a trial of at least one antidepressant medication. The goal of this study is to translate the knowledge learned from neurophysiological studies of insomnia to the clinical treatment of insomnia using TMS as the primary modality.

### Specific Aim I:

Compare the change in insomnia scores on Pittsburgh Sleep Quality index between baseline and end of the study with sequential bifrontal low frequency TMS in patients with primary chronic insomnia using daily stimulation over a period of 3 weeks (15-week days).

### ***Hypothesis I (Between Group Hypothesis):***

Sequential bifrontal low frequency TMS (1 Hz), by exerting an inhibitory effect on cortical hyper-arousal, will lead to improvement in patients with chronic insomnia as measured by PSQI.

Subjective and objective sleep parameters may vary in patients with insomnia. Patients with insomnia tend to underestimate their total sleep time (TST) To quantify a possible discrepancy between subjective and objective sleep parameters like sleep onset latency (SOL) and TST which may be affected by TMS, we propose to assess both objective and subjective measures of sleep onset, sleep continuity and total sleep time.

### ***Specific Aim II:***

Compare the change in Insomnia severity index (ISI), TST, SOL, wake after sleep onset (WASO) as measured on ISI, actigraphy and sleep diaries between baseline and end of treatment in subjects receiving low frequency TMS.

### ***Hypothesis II (Objective vs. Subjective changes in sleep):***

Because there are no data on TMS and insomnia, we are proposing the null hypothesis. TMS treatment does not differentially affect subjective and objective sleep parameters.

**Significance:** Insomnia is a clinical problem of significant public health importance. It is a huge burden on healthcare as it increases healthcare costs. Insomnia has also been invoked in causation of other medical and psychiatric disorders, cognitive impairments, accidents, absenteeism and reduced quality of life. Effective treatment of insomnia involves multi-modal treatments that are not easily available. Most medications used in the treatment of insomnia are associated with adverse effects and lose efficacy with long-term use. There is need to develop treatments for insomnia that are easy to administer, safe and well tolerated by patients. A diffuse cortical excitability, as measured by various physiological parameters, has been seen in chronic insomnia. This inappropriate physiological arousal is seen as high frequency EEG activation, abnormal hormone secretion, high whole body and brain metabolic activation, elevated heart rate and sympathetic nervous system activation during sleep.

TMS is a non-invasive brain stimulation technique that can be used to investigate directly the excitability level of human cerebral cortex. Van der Werf et al studied 16 patients with chronic insomnia and 14 matched controls using absolute and relative motor evoked potentials in response to single and paired pulse TMS. They found increased absolute response but reduced relative response to paired pulse stimulation at long interpulse intervals. This is indicative of diffuse cortical hyper-arousal but disturbed intra-cortical excitability in patients with chronic insomnia. High frequency TMS (10 Hz) has been shown to be activating whereas low frequency TMS (1Hz) has been shown to be inhibitory.

TMS has been shown to be safe and effective treatment. It is approved as a treatment of depression in patients who have not responded to a trial of one antidepressant medication. Our preliminary studies have prepared us to undertake this new study. A review of clinical records from our sleep clinic revealed that insomnia is a common presenting feature. It was more commonly seen in patients with co-morbid depression. Presenting feature of insomnia alerts the clinician to look for co-morbid depression. A review of preliminary data from 14 patients receiving treatment with high frequency (10Hz) left prefrontal cortex TMS for depression in our TMS therapy clinic shows that symptoms of depression and insomnia improve with TMS as seen on Montgomery Asberg depression rating scale (MADRS) scores. This improvement did not correlate with overall improvement in depressive symptoms in all patients. There was no worsening of depressive and insomnia scores with TMS as measured on MADRS scores. We think that current stimulation technique and parameters used in TMS therapy for depression will be counter-therapeutic or ineffective for insomnia, which is one of the rationales for proposed low frequency TMS. Both high and low frequency TMS treatment has been found to be safe

and effective in our review of neuropsychiatric disorders other than depression, however, it is putative that bilateral low frequency TMS (1Hz) and not high frequency (TMS) will lead to improvement in patients with chronic insomnia by exerting an inhibitory effect on hyper-excitable cortical state. If this pilot study shows effectiveness of low frequency TMS in insomnia, we will seek extramural funding and possibly additional multi-site collaboration to test our findings in a larger randomized placebo controlled clinical trial. This will lay the groundwork for establishing the role of low frequency TMS, an easy-to-administer, non-invasive treatment, for this huge clinical and public health problem.

***Innovation:***

This study offers a novel method to utilize the knowledge gained from neurophysiological studies of TMS in clinical treatment of insomnia. This study is the first of its kind that will explore sequential bifrontal low frequency TMS as a treatment modality for chronic insomnia.

***Approach:***

***a) Research Design and Methodology:***

This is a one year, prospective, open label pilot study to compare sequential bilateral low frequency TMS in patients with chronic insomnia. Subjects with chronic insomnia will be offered enrollment in this study to receive sequential low frequency (1Hz) bifrontal cortical TMS stimulation. We propose to enroll 25 patients so that we will have complete data on 20 patients with primary/chronic insomnia.

***b) Inclusion criteria:***

1. Patients referred for evaluation and management of insomnia to our sleep disorders clinic will be offered enrollment in this study.
2. Patients must meet DSM IV criteria for Primary insomnia.
3. Aged 21-65 years to target relatively healthy adults.

***c) Exclusion criteria:***

- 1) Patients with Major depressive disorder.
- 2) Substance abuse in last two weeks.
- 3) No Psychotropic medication changes 2 weeks before start of TMS treatment and no changes during the 3 week treatment period.
- 4) Patients with a major medical or psychiatric disorder that may be causing or contributing to insomnia: bipolar disorder, psychosis, anxiety disorders, dementia, seizure disorder and chronic pain.
- 5) Patients with ferromagnetic material in their head or within 30 cm of the coil will be excluded.

Subjects may withdraw from the study at any time. Subjects will be withdrawn who do not comply with the ratings and procedures or have an adverse event or a new clinical situation that necessitates their withdrawal from study as deemed necessary by PI.

***d) Procedure:***

Prior to any beginning any study activities subjects will sign the informed consent. Subjects will then be asked to sign a release of information so that the study team can review the medical record of each participant. Baseline clinician rating and clinical assessment and examination will consist of medical records review to obtain information about medical conditions, medications, and physical examination findings. This information will be documented in research files of the subjects. We will also record routine demographic information such as marital status and education as well as age, sex, height and weight. Patients will be assessed weekly to monitor and rate their symptoms. Patients who qualify for enrollment in this study will receive sequential

bilateral bifrontal low frequency TMS stimulation daily on weekdays for three weeks. Stimulation parameters are: 1Hz, 80-120% motor threshold, inter-train interval: 0, 40 minutes of treatment on each left and right prefrontal cortex. Insomnia has shown to be a disorder of hyperarousal. Neuroimaging studies of various brain areas have been shown to reflect this hyperarousal including hypothalamus, thalamus, amygdala, hippocampus and prefrontal cortices. Wake after sleep onset has been correlated with increased glucose metabolism in frontal cortices along with other subcortical areas. Frontal cortices have been more implicated in hyperarousal compared to other cortical areas. Transcranial magnetic stimulation is relatively safe and non-invasive method of stimulating cortical brain areas. Therefore, we are choosing stimulating frontal cortices with TMS to evaluate for effect on insomnia.

Motor threshold will be calculated on left side and right side and will be stimulated at approximately the same distance as the center of the coil from the midline. The primary outcome variable will be the change in Pittsburgh Sleep Quality Index (PSQI) between baseline and end of the treatment.

For the TMS procedure all subjects will be asked to remove glasses, earrings or metal objects within 30 cm of the coil prior to treatment. Noise canceling ear plugs will be provided. A physician who is trained in TMS will administer and monitor the treatment. The study physicians will monitor closely for adverse events and will ensure that all rating scales are completed at the appropriate times.

**e) Instruments:**

Subjects will be rated weekly on PSQI, Insomnia severity index, CGI and MADRS. They will be requested to keep daily sleep diaries and wear actigraphy devices throughout the three week period of study.

**Insomnia severity Rating Index:** This instrument has been shown to be a reliable and valid to detect cases of insomnia in the population and is sensitive to treatment response in clinical population. It is a 7-item self-report questionnaire assessing the nature, severity, and impact of insomnia. The usual recall period is the “last month” and the dimensions evaluated are: severity of sleep onset, sleep maintenance, and early morning awakening problems, sleep dissatisfaction, interference of sleep difficulties with daytime functioning, noticeability of sleep problems by others, and distress caused by the sleep difficulties. A 5-point Likert scale is used to rate each item (e.g., 0 = no problem; 4 = very severe problem), yielding a total score ranging from 0 to 28. The total score is interpreted as follows: absence of insomnia (0-7); sub-threshold insomnia (8-14); moderate insomnia (15-21); and severe insomnia (22-28). Three versions are available—patient, clinician, and significant others—but the present paper focuses on the patient version only. Previous studies have reported adequate psychometric properties for both the English and French versions.

**PSQI:** Pittsburgh Sleep Quality Index is 10-item scale evaluating various domains of subjectively reported sleep. The score can be between 0-21. A score of less than 5 indicates good sleep quality whereas a score greater than 5 indicates poor sleep quality.

**CGI:** Clinical Global Impression is an easily administered clinician rating scale assessing overall clinical impression.

**MADRS:** Montgomery Asberg Depression Rating Scale is a 10-item questionnaire used by clinicians to rate the severity of depression.

**Mini Mental State Exam (MMSE):** assesses potential impairment in cognition (thinking)

**Sleep diary:** Sleep diaries are used both in research and clinical practice in the treatment of insomnia. Diaries will be completed daily by patients, reporting bedtime, wake up time, awakenings and various other daytime activities.

**Actigraphy:** It is a wrist device that is worn like a watch. It records physical activity and light exposure. It provides objective information about the rest-activity cycle. It is also useful to derive objective sleep parameters like sleep onset latency (SOL), total sleep time (TST) and wake-after-sleep onset (WASO).

**Epworth Sleepiness Scale (ESS):** 8-item self-administered questionnaire that provides a measurement of the general level of daytime sleepiness.

**Pittsburgh Insomnia Rating Scale (PIRS):** 66-item self-administered questionnaire that assesses severity of insomnia.

Schedule of Events	Day 1	Day 2-6	Day 7	Day 8-13	Day 14	Day 15-20	Day 21
Informed Consent	X						
Physical Exam	X						
Psychiatric interview	X						
Vital Signs	X						
Insomnia severity Rating Index	X		X		X		X
Pittsburgh Sleep Quality Index	X		X		X		X
MADRS	X		X		X		X
CGI	X		X		X		X
MMSE	X		X		X		X
Sleep diary	X	X	X	X	X	X	X
Actigraphy	X	X	X	X	X	X	X
TMS treatment	X	X	X	X	X	X	X
Adverse Events and Concomitant Medications	x	x	x	x	x	x	x

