#### **Potential problems:**

A potential problem could be worsening of insomnia during TMS treatment. We will monitor subjects weekly and rate their insomnia and depressive symptoms. A MADRS score above 9 would necessitate a clinical interview to assess for depression. If subjects are found to have clinical depression, they will be released from the study and offered treatment in our outpatient clinic. We will study about 25 patients to get 20 completers. Patients with various sleep disorders including insomnia are referred to our sleep disorders' clinic. We see about 70 new patients a month. About 15% of these patients are found to have insomnia. These patients are of all ranges. We expect to enroll the requisite number of patients in the study period. We will hold regular study related meetings with all study personnel to document progress.

If a seizure or other medical condition arises during the course of TMS treatment, the study physicians will ensure appropriate medical evaluation.

**Data Analysis and Statistical Methods:** We shall compare baseline to post treatment via a one-sample t-test, using a two-sided P-value <0.05 to declare significance. The Total Pittsburgh Sleep Quality Index (PSQI) will be the primary outcome variables. Other outcomes will be analyzed in a similar manner, but the study is powered strictly around PSQI. Significant findings on secondary variables will not be considered as definitive.

**Power for a sample size of N=20 completing subjects:** Based on results from the study of a large cohort of poor sleeping subjects had a cross sectional mean PSQI of 11.6 (SD=2.5). Conservatively assuming that the repeated measures correlation is between 0.70 and 0.80 (Repeat measures assume 50-65% of the variation), the study has 80% power to detect 0.66 standard deviations of the paired difference. This translates to sensitivity to a 1.04 to 1.28 unit

difference in pre to post mean (9%-11% change in the mean PQSI). Final sample size will be 25 subjects to allow for a dropout rate of 20%. Every attempt will be made to collect the PSQI on both days, whether the subject is compliant or not. We shall approximate intent-to-treat as closely as possible, including attempts to get non-compliers to do the post-test and carrying the last observation forward.

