Other sleep parameters will be evaluated as secondary endpoints, and a descriptive analysis of responders (reduction by at least 30%) to non-responders will help identify subgroups to be targeted in future. We will analyze the differences in outcome between subjective (PSQI scores, ISI, SOL on PSQI and sleep diaries, TST on sleep diaries and PSQI) and objective measures (actigraphy computed SOL, TST and WASO) between the baseline and end of treatment. We will also analyze the predictive value of insomnia symptoms and severity in predicting treatment efficacy of TMS as a secondary variable. Given the small sample size, we may see differences/trends in this regard that will need to be studied in larger studies. Last Observation Carry Forward (LOCF) strategy will be used to study dropouts. We will also contact those subjects that drop out to ask for the reason for drop-out.

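### If the ISI keeps the only recall period the protocol gives for it (a month), 8-10 of the 28-30 nights behind the Day 21 score precede treatment, and any true ISI change tends to be understated

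*Combined protocol and SAP*

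**What the plan says.** Section e) Instruments sets the frequency: "Subjects will be rated weekly on PSQI, Insomnia severity index, CGI and MADRS". In the same section, the description of the ISI reads "The usual recall period is the “last month” and the dimensions evaluated are", followed by the item topics. This is the only ISI recall period in the document. Nothing says that the form used in this trial will carry a shorter one.

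The table headed "Schedule of Events" marks the ISI on Days 1, 7, 14 and 21. TMS is marked from Day 1, and no visit follows Day 21. The table does not say whether the Day 1 ISI comes before or after the first session.

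Under Specific Aim II, the ISI is one of the outcomes to be analysed: "Compare the change in Insomnia severity index (ISI), TST, SOL, wake after sleep onset (WASO) as measured on ISI, actigraphy and sleep diaries", with the end of treatment set against baseline. For missing end-of-treatment data, the statistical text (printed under Potential problems) says "Last Observation Carry Forward (LOCF) strategy will be used to study dropouts". On numbers it says "Final sample size will be 25 subjects to allow for a dropout rate of 20" per cent. The same text calls significant secondary findings not definitive and plans to seek a post-test from non-compliers.

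**The concern.** A score with month-long recall, collected at the end of a three-week course, mixes treated nights with nights before treatment began. The end-of-treatment ISI then partly re-measures the baseline period. The baseline-to-end difference, which is what Aim II asks for, is pulled toward zero. This holds for improvement and for worsening.

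The mixture is heavier at the interim ratings. It would enter the Aim II comparison wherever last observation carried forward (LOCF) substitutes a Day 7 or Day 14 score for a missing Day 21 score. If the form does not fix the window, no later analysis can separate the two parts of the score.

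**Working it through.** The plan gives no figure for recall overlap, so there is none to reproduce. The check is a count of nights.

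**Inputs**
- Recall window: a month (e) Instruments). The document gives no number of nights; I assume k = 28 to 30 and show 31 as a sensitivity.
- Rating days D = 7, 14, 21, with the first session on Day 1 (schedule table).
- Enrolment 25, dropout 20% (power text).

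**Step 1. Nights before treatment.** The first night after a session is the night of Day 1. By the rating on Day D, D - 1 nights have passed since the first session (weekend nights included). Pre-treatment nights = k - (D - 1).

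| Rating | Nights since first session | k = 28 | k = 30 | k = 31 |
|---|---|---|---|---|
| Day 7 | 6 | 22 | 24 | 25 |
| Day 14 | 13 | 15 | 17 | 18 |
| Day 21 | 20 | 8 | 10 | 11 |

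Counting 19 or 21 treated nights at Day 21 instead of 20 moves the 8-10 only to 9-11 or 7-9.

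**Step 2. Share of the effect recorded, nights weighted equally.** For an effect that is immediate and constant from the first night (assumption), the share is (D - 1)/k.
- Day 21: 20/28 = 71% to 20/30 = 67%.
- Day 14: 13/28 = 46% to 13/30 = 43%.
- Day 7: 6/28 = 21% to 6/30 = 20%.

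**Step 3. Share recorded if recent nights count more.** Weight the night i nights back from the latest by 0.5^(i/h), where h is a half-life in nights (assumption; the document gives no basis for any value). The share is (1 - 0.5^((D - 1)/h)) / (1 - 0.5^(k/h)). With k = 30:

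| Rating | h = 14 | h = 7 | h = 3 |
|---|---|---|---|
| Day 21 | 81% | 91% | 99% |
| Day 14 | 61% | 76% | 95% |
| Day 7 | 33% | 47% | 75% |

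**Step 4. In ISI points.** Take a true fall of 4 points, from 18 to 14, which crosses from moderate to sub-threshold on the bands in e) Instruments. At Day 21 it would be recorded as 4 × 0.667 = 2.7 to 4 × 0.714 = 2.9 points with equal weights. With recency weights it would be 4 × 0.812 = 3.2 to 4 × 0.991 = 4.0 points.

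**Step 5. Reach of LOCF.** 0.20 × 25 = 5 patients at most under the planned dropout, and only if none of them gives a post-test.

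**Step 6. A 7-day window.** Pre-treatment nights = 7 - (D - 1), not below zero: 1 at Day 7, none at Day 14 or Day 21.

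**The case against.** **The month is background, not an instruction.** The sentence describes how the ISI is usually used and sits in a general account of the instrument. The trial's own instruction is only to rate weekly. This stands: use of the unmodified window is not proven, and the point is therefore conditional. But it is the only window the document offers, and if a shorter one is intended the protocol needs to say so.

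**The size is assumption.** This also stands. Neither equal weighting nor any half-life comes from the document, and the loss at Day 21 could be as small as 1%. Several ISI items (dissatisfaction, interference, distress) are global appraisals that may not average over nights. In the other direction, a gradual onset would enlarge the shortfall against the state at the end of treatment.

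**The stakes are low.** Agreed. The ISI is secondary, the study is powered only on the PSQI, and dilution toward no change would not create a false positive.

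**Stronger readings the documents do not support.**
- *That Hypothesis II is compromised.* The plan says "We will analyze the differences in outcome between subjective (PSQI scores, ISI, SOL on PSQI and sleep diaries", among others, and objective measures, and hypothesises that "TMS treatment does not differentially affect subjective and objective sleep parameters". A reader might infer that the ISI window would produce a false subjective-objective gap. It does not follow. Actigraphy also starts on Day 1, so it has essentially no pre-treatment night. Under an immediate constant effect, its own baseline-to-end change would be near zero while the ISI still recorded a share, so the gap could run the opposite way. Diary sleep latency and total sleep time are listed as subjective measures too, and they carry no monthly window.
- *That the primary endpoint is diluted.* The document states no recall period for the PSQI, so no count can be made for it.
- *That the reported ISI change will be too small overall.* Open-label expectancy could push the other way by an unknown amount. Only this one component is claimed.

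**Conclusion.** The concern holds in conditional form. With the ISI's stated usual recall left unmodified, 8-10 of 28-30 nights at Day 21 precede treatment, and the Aim II change tends to be understated. The night counts follow from the schedule plus the assumed length of a month. The effect size does not: the 67%-71% and the upper figure of about 99% both assume an immediate constant effect, and they differ only in how patients are assumed to weight nights. Interim scores are more diluted, which matters for the few patients whose Day 7 or Day 14 score would be carried forward. No loss of power is claimed. This is a cheap improvement to a secondary measure, not a threat to the trial's main result.

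**What to change.** In e) Instruments, state that the ISI asks about the past 7 days at every rating, baseline included, and print that wording on the ISI form. State also that the Day 1 ISI is completed before the first TMS session.

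The cost is one protocol sentence and one form header. There are two downsides. Scores on a 7-day form are less comparable with the published severity bands that the protocol quotes. A one-week baseline is also somewhat noisier than a one-month one. Added regression to the mean should be small, because entry rests on a DSM-IV diagnosis with no ISI cut-off.

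Leave the PSQI form unchanged. The document gives no recall period for it, and altering the primary instrument would weaken the link to the planning mean (11.6), SD (2.5) and correlation (0.70-0.80). A later ISI rating, at least a month after the first session, would also remove the pre-treatment nights, but it needs an added visit and would take in nights after the course has ended.

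### No untreated actigraphy or diary window is scheduled or defined, so the baseline comparison in Specific Aim II could be an on-treatment change

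*Combined protocol and SAP*

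**What the plan says.** All references are to the combined protocol and SAP.

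- **Specific Aim II** names as outcomes, besides the ISI, "TST, SOL, wake after sleep onset (WASO) as measured on ISI, actigraphy and sleep diaries between baseline and end of treatment".
- **Data Analysis and Statistical Methods** plans to set subjective measures against "objective measures (actigraphy computed SOL, TST and WASO) between the baseline and end of treatment". The subjective side includes "SOL on PSQI and sleep diaries, TST on sleep diaries and PSQI". It also says that the study is powered on PSQI alone and that significant secondary findings will not be taken as definitive.
- **Hypothesis II** is framed as a null: TMS does not act differently on subjective and objective sleep measures.
- **d) Procedure** places consent first: "Prior to any beginning any study activities subjects will sign the informed consent". Treatment is "TMS stimulation daily on weekdays for three weeks".
- **e) Instruments** asks participants to "keep daily sleep diaries and wear actigraphy devices throughout the three week period of study".
- **Schedule of Events** begins at Day 1 and has no screening or run-in column. Consent, ISI, PSQI, diary, actigraphy and TMS are all first marked on Day 1. Diary, actigraphy and TMS are then marked in every column to Day 21.

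**The concern.** A change from baseline needs a baseline measured before treatment. For actigraphy and the diary, the plan starts recording on the day it starts treating. Actigraphy is the only objective sleep measure listed in this uncontrolled, open-label trial, so it is the main check on self-report. If its baseline nights are already treated nights, the planned comparison misses whatever part of an effect is present by then.

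Hypothesis II has a further problem. PSQI and ISI can have a pre-session value on Day 1, although the plan does not state that order. Actigraphy has none as scheduled. A difference between subjective and objective change could then come from unequal baselines and not from TMS. Untreated nights cannot be recovered once treatment has begun, so the matter has to be settled before enrolment.

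**Working it through.** **1. The plan's own figure.** The documents give no figure for actigraphy or diary outcomes; the only power statement concerns PSQI. With 20 completers, a two-sided 0.05 one-sample t-test and a standardised change of 0.66, exact noncentral-t power is 0.799, against the stated 80%. The SD of the difference is 2.5 × √(2(1 − r)), which is 1.936 at r = 0.70 and 1.581 at r = 0.80. Multiplying by 0.66 gives 1.28 and 1.04 units, or 11.0% and 9.0% of 11.6. Enrolment is 20/(1 − 0.20) = 25. All stated figures reproduce, and nothing below changes them.

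**2. What the aim needs against what is collected.**

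| Needed | Scheduled |
|---|---|
| Actigraphy before the first session | First mark on Day 1, the same column as the first TMS mark |
| Diary before the first session | First mark on Day 1; an entry that day could at most recall the night before |
| Device and diary issued beforehand | Not possible before consent, which is also on Day 1 |
| Nights forming the baseline value | Not stated |
| Nights forming the end-of-treatment value | Not stated |

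Taken as written, the count of untreated actigraphy nights is 0.

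**3. A looser reading of the table.** The TMS row marks all 21 days, whereas Specific Aim I describes "daily stimulation over a period of 3 weeks (15-week days"). Suppose the 15 weekday sessions fall within the 21 recorded days. Any 21 consecutive days contain exactly 15 weekdays, so the first weekday must be the first session. Untreated actigraphy nights by weekday of Day 1 are:

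- Monday to Friday: 0
- Saturday: 2
- Sunday: 1

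The maximum is 2. The diary could add one more by recall. Nothing in the plan says that such nights would be used as the baseline.

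**4. Illustration only.** The plan gives neither a time course nor analysis windows. Assume that week 1 serves as baseline and week 3 as end of treatment, and express the result as a share of the untreated-to-week-3 change.

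- Linear build-up, effect k/21 on night k: week 1 mean 4/21 = 0.190, week 3 mean 18/21 = 0.857. Share captured = (18 − 4)/18 = 0.778, about 78%.
- Linear to full effect by night 7, then flat: week 1 mean 4/7 = 0.571, week 3 mean 1. Share captured = 3/7 = 0.429, about 43%.
- Full effect from night 1: both means are 1. Share captured = 0.
- No effect until after night 7: week 1 mean 0. Share captured = 100%.

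These cases show that the answer depends on an unstated time course. They are not estimates for this trial.

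**The case against.** **The schedule is loose, so Day 1 should not be read too literally.** This stands in part. A row that marks TMS on all 21 days cannot be relied on to fix the first session, which is why the point is that the comparison could be an on-treatment change, not that it must be. But the most generous calendar yields only 2 untreated actigraphy nights, and the windows are undefined on any reading.

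**These are secondary outcomes in a pilot.** This stands as a limit on importance. However, calling findings non-definitive speaks to the strength of evidence. It does not supply a baseline for a named aim that is defined as change from baseline.

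**Diary and actigraphy cover the same nights, so their contrast could still test Hypothesis II.** A reader might infer this, but it does not hold. Shared nights do not help if subjective and objective sleep change at different speeds, which is close to what the hypothesis asks. If both responded at once, both on-treatment changes would be zero and the contrast uninformative. The diary may also have one recalled untreated night that actigraphy lacks.

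**A reader might want to size the ISI-versus-actigraphy mismatch.** The documents do not allow it. They state only that "The usual recall period is the “last month" and do not say which recall period the weekly ISI uses. With a month's recall, an ISI on Day 21 would still reach back to untreated nights even if actigraphy had a perfect baseline. That part of any mismatch is not caused by the missing window.

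**Conclusion.** The point holds as a gap in the design of a secondary aim and should be fixed. As scheduled, 0 untreated actigraphy nights precede the first session. The number is at most 2 if 15 weekday sessions fit the 21 days with a weekend start, and the diary could have one more by recall. Neither the baseline nor the end-of-treatment nights are defined.

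A reader might conclude that the actigraphy and diary changes will certainly be understated. The documents do not support that. Understatement requires a beneficial effect already present in the nights used as baseline, and first-night or device-adaptation effects could push the change either way. The 78% figure rests on an assumed linear course and assumed windows.

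Nor does the point reach the primary result: the PSQI analysis, its power and the sample size of 25 are untouched. No loss of power is claimed for the secondary outcomes.

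**What to change.** Add a column to the Schedule of Events after consent and before the first session, with actigraphy and diary recording for several nights; the number is the sponsor's choice. Define baseline as the mean of those nights, and end of treatment as the mean of the same number of final nights. State that the Day 1 questionnaires are completed before the first session.

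The cost is up to about a week's delay per participant, possibly one extra contact to issue devices, and possibly slightly more dropout before treatment on top of the 20% already allowed. The devices and diaries are already in the study.

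If a run-in is not feasible, describe the actigraphy and diary results as on-treatment change and state that Hypothesis II can be addressed only descriptively. This costs a few sentences but gives up the untreated comparison for the objective measures.

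Separately, the TMS row, which marks every day, and the weekday schedule in Specific Aim I and d) Procedure must be reconciled.
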